Exclusion criteria #21 has also been removed under this amendment. In embryofetal development studies with asciminib, fetal malformations (cardiac malformations) and increased visceral and skeletal variants were observed in rats and increased incidence of resorptions indicative of embryo-fetal mortality and a low incidence of cardiac malformations indicative of dysmorphogenesis were observed in rabbits. Asciminib is not genotoxic. As published in the literature, small molecules can distribute to seminal fluid and the seminal accumulation suggested is semen/plasma ratios up to 11.3 (Klemmt and Scialli 2005). According to the FDA guidance, in general, there is increased concern for reproductive or developmental toxicity in humans for relative exposure ratios (animal: human) that are < 10 and decreased concern for exposure ratios > 25 (FDA Guidance for Industry 2011). The calculations for the asciminib safety margin were done based on C_{max} (plasma) seen in patients at a dose of 200 mg BID (C_{max} 6843 ng/ml). Safety margin calculation based on the embryo-fetal development study in rats was 768 and safety margin calculation based on the embryo-fetal development study in rabbits was 894. In conclusion, for asciminib, as outlined above, the safety margins are well above 25 and therefore no embryo- and fetotoxicity effects can be anticipated via seminal fluid. Removal of male contraception is in line with the Bosutinib USPI and SmPC.

In addition, patients can be re-screened up to three times for the study, instead of once. The patient population being investigated in this study is heavily pre-treated and patients might not have other treatment options outside the trial. There can be many intolerance-related temporary conditions resulting in ineligibility for the trial.

Recruitment period extension has been reflected in the VES table. Study length has changed with introduction of switch option for patients failing bosutinib treatment.

Patients enrolling in this trial will present a high disease burden after failure of previous therapies. Myelosuppression during TKI targeted treatment is a very common effect observed due to the suppression of the leukemic clone; this effect is also extended to hematopoiesis of

stem cells and progenitors (Stegmann et al 2016). For this reason, the recovery period for cytopenias has been extended from 28 to 42 days in order to allow for sufficient time to recover from suppression and to re-populate the bone marrow.

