 - Table 3-1 Objectives and related endpoints.
 - Section 10.1.6 Other analysis sets.
 - Section 10.6 Exploratory objectives:
 - Section 10.6.1 Exploratory efficacy objectives.
 - Section 10.6.1.1 Data analysis of exploratory efficacy objectives.
- Reference for concomitant medications with a “known risk of TdP” has been updated to www.crediblemeds.org/
 - Protocol summary
 - Section 5.3 Exclusion criteria
 - Section 6.3.2 Dose adjustments for QTcF prolongation
 - Section 6.4.3 Prohibited concomitant therapy
- [REDACTED]
- [REDACTED]
- [REDACTED]
- [REDACTED]
- Section 5.2 Inclusion criteria and protocol summary: updated inclusion criteria to reflect the changes below:
 - Inclusion Criteria #3: As referenced above, the requirement of BCR-ABL1 ratio $\geq 1\%$ IS has been decreased to BCR-ABL1 ratio $> 0.1\%$ IS at the time of screening for patients intolerant to previous TKI.
 - Inclusion Criteria #10: Potassium increase of up to 6.0 mmol/L is accepted at study entry if associated with creatine clearance within normal limits. Calcium increase of up to 12.5 mg/dl or 3.1 mmol/L is acceptable at study entry if associated with creatinine clearance within normal limits. GFR replaced by Creatinine clearance (calculated using Cockcroft-Gault formula) in order to maintain consistency throughout the protocol as creatinine clearance is already calculated based on inclusion criteria #7.
 - Inclusion Criteria #11: As study eligibility is assessed during screening with BCR-ABL1 PCR quantification via international scale this requirement was added as

clarification. Measurement according to international scale is only possible for typical BCR-ABL1 transcripts.

- Section 5.3 Exclusion Criteria and Protocol summary: updated exclusion criteria to reflect the following changes:
 - Exclusion Criteria #14: Removal of P-gp as a moderate or strong inhibitor of CYP3A as P-gp inhibitors are no longer prohibited per updated USPI, and SmPC
 - Exclusion Criteria #19: Duration of the use of highly effective methods of contraception after the last dose of bosutinib has been defined to align with the latest bosutinib USPI.
 - Exclusion Criteria #21 Removal of this criteria in order to align with updated pre-clinical data.
- Section 6.3.1 Dose modification and dose delay: The recovery period for cytopenias has been extended from 28 to 42 days in order to allow for sufficient time to recover from suppression and to re-populate the bone marrow.

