 - Removal of P-gp inhibitors from Table 14-3 Prohibited concomitant medications for bosutinib arm.
 - Addition of new medications to Category Torsade de pointe (TdP) TdP/QT risk: Known.
 - Addition of new category, TdP/QT risk: Possible.
 - Addition of new category, TdP/QT risk: Conditional.

IRBs/IECs

A copy of this amended protocol will be sent to the Institutional Review Board (IRBs)/Independent Ethics Committee (IECs) and Health Authorities.

The changes described in this amended protocol require IRB/IEC approval prior to implementation.

The changes herein affect the Informed Consent. Sites are required to update and submit for approval a revised Informed Consent that takes into account the changes described in this protocol amendment.

Amendment 2 (13-Jul-2018)

Amendment rationale

As of 29-Jun-2018, this study has been submitted in 25 and approved in 24 countries. Eighty five (85) sites were initiated, 67 patients were screened and 38 patients were randomized in the study.

The primary purposes of the amendment are:

The frequency of bone marrow aspirate (BMA) to perform cytogenetic analysis has been decreased in accordance with treatment guidelines (European Leukemia Network (ELN) Guidelines ([Baccarani et al 2013](#)), [National Comprehensive Cancer Network \(NCCN\)](#) (Clinical Practice Guidelines in Oncology-Chronic Myeloid Leukemia v4.2018)). Initially BMAs were foreseen at screening, every 24 weeks thereafter and at end of treatment. With the protocol amendment BMA is no longer needed for patients that have achieved MMR during study, however BMA assessment is requested at the time of end of treatment for biomarker analysis.

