6.3 Dose modifications

6.3.1 Dose modification and dose delay

For patients who do not tolerate the protocol-specified dosing schedule, dose interruptions and/or reductions are either recommended or mandated in order to allow the patient to continue the study treatment.

These dose modifications are summarized in [Table 6-2](#). The dose reduction indicated as “recommendations” are provided to assist investigators in the event the patient experiences toxicity. However, deviations from “mandatory” dose interruptions and/or reductions are not allowed and mandatory interruptions or reductions must be strictly followed. Re-escalation to asciminib 40 mg BID is permitted if a change in the patient’s individual benefit/risk assessment at the lower dose level is seen. Re-escalation will be allowed only once for any given patient on the asciminib arm per protocol. Permanent treatment discontinuation is mandatory for specific events indicated as such in [Table 6-2](#). Any dose changes must be recorded on the Dosage Administration Record eCRF.

A patient must discontinue treatment with either asciminib or bosutinib if, after treatment is resumed at a lower dose level, the toxicity recurs with the same or worse severity, except for recurrence of cytopenias ([Table 6-2](#)). If a patient requires a dose interruption of > 28 days for each non-hematologic toxicity, then the patient must be discontinued from the study treatment. If a hematologic toxicity (cytopenia Grade 3 or 4) lasts for more than 42 days without recovery to at least a Grade 2, despite TKI interruption and adequate management (including hematopoietic growth factors), then the patient must be discontinued from the study treatment.

Table 6-2 Criteria for dose reduction/interruption and re-initiation of asciminib and bosutinib treatment for adverse drug reactions

[figure not shown]
Dose modifications for both asciminib and bosutinib		
Please note that if a patient requires a dose interruption of > 28 days for each toxicity, then the patient must be discontinued from the study treatment		
Worst toxicity CTCAE Grade 4.03	Asciminib	Bosutinib
Investigations (Hematologic) If a hematologic toxicity (cytopenia Grade 3 or 4) lasts for more than 42 days without recovery to at least a Grade 2, despite TKI interruption and adequate management (including hematopoietic growth factors), then the patient must be discontinued from the study treatment.		
Neutropenia (ANC)		

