Grade 1 (ANC < LLN – 1.5 x 10 ⁹ /L)	Recommendation: Maintain dose level	Recommendation: Maintain dose level
Grade 2 (ANC < 1.5 – 1.0 x 10 ⁹ /L)	Recommendation: Maintain dose level	Recommendation: Maintain dose level
Grade 3 (ANC < 1.0 – 0.5 x 10 ⁹ /L)	Mandatory: Hold dose until resolved to ≤ Grade 2 (recheck CBC 2x/week), then: if resolved in ≤ 14 days, then maintain dose level If resolved in > 14 days, then reduce dose ↓ 1 dose level	Mandatory: Hold dose until resolved to ≤ Grade 2 and platelets ≤ Grade 2 (recheck CBC 2x/week), then: if resolved in ≤ 14 days, then maintain dose level If resolved in > 14 days, reduce dose ↓ 1 dose level
Grade 4 (ANC < 0.5 x 10 ⁹ /L)	Mandatory: Hold dose until resolved to ≤ Grade 2, (recheck CBC 2x/week), then: if resolved in ≤ 14 days, then maintain dose level if resolved in > 14 days, then reduce dose ↓ 1 dose level	Mandatory: Hold dose until resolved to ≤ Grade 2 and platelets ≤ Grade 2 (recheck CBC 2x/week), then: if resolved in ≤ 14 days, then maintain dose level if resolved in > 14 days, then reduce dose ↓ 1 dose level
Febrile neutropenia (ANC < 1.0 x 10 ⁹ /L, fever ≥ 38.5°C)	Mandatory: Hold dose until resolved, then reduce dose ↓ 1 dose level	Mandatory: Hold dose until resolved, then reduce dose ↓ 1 dose level
Thrombocytopenia		
Grade 1 (PLT < LLN – 75 X 10 ⁹ /L)	Recommendation: Maintain dose level	Recommendation: Maintain dose level
Grade 2 (PLT < 75 - 50 x 10 ⁹ /L)	Recommendation: Maintain dose level	Recommendation: Maintain dose level

[figure not shown]
Dose modifications for both asciminib and bosutinib		
Please note that if a patient requires a dose interruption of > 28 days for each toxicity, then the patient must be discontinued from the study treatment		
Worst toxicity CTCAE Grade 4.03	Asciminib	Bosutinib
Grade 3 (PLT < 50 - 25 x 10 ⁹ /L)	Mandatory: Hold dose until resolved to ≤ Grade 2 (recheck CBC 2x/week), then: if resolved in ≤ 14 days, then maintain dose level if resolved in > 14 days, then reduce dose ↓ 1 dose level	Mandatory: Hold dose until resolved to ≤ Grade 2 and neutrophils ≤ Grade 2 (recheck CBC 2x/week), then: if resolved in ≤ 14 days, then maintain dose level if resolved in > 14 days, then reduce dose ↓ 1 dose level

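### The Table 6-2 header orders a stop after 28 days' interruption for any toxicity, while section 6.3.1 and the table's own hematologic sub-header allow Grade 3/4 cytopenia 42 days

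*Combined protocol and SAP*

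**What the plan says.** Three statements in the current protocol set the point at which a prolonged dose hold becomes a permanent stop.

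- **Section 6.3.1, text.** The 28-day stop applies to a "dose interruption of > 28 days for each non-hematologic toxicity".
- **Section 6.3.1, text, and again the hematologic sub-header of Table 6-2.** Cytopenia has its own limit: "If a hematologic toxicity (cytopenia Grade 3 or 4) lasts for more than 42 days without recovery to at least a Grade 2", despite interruption and adequate management, the patient must come off study treatment.
- **Table 6-2, header.** The instruction is general: "if a patient requires a dose interruption of > 28 days for each toxicity, then the patient must be discontinued from the study treatment". It names no exception.

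The neutropenia and thrombocytopenia rows of Table 6-2 make it mandatory to hold the dose while Grade 3 or 4 cytopenia persists. If recovery to Grade 2 or better takes longer than 14 days, treatment restarts one dose level lower.

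**The concern.** Both limits are mandatory, and for cytopenia they differ. A site that reads the table header literally would permanently stop a patient whom section 6.3.1 allows to recover and resume.

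That decision carries through to the efficacy data. Under sections 10.4.3, 10.5.1 and 10.5.2, a patient who discontinues randomized treatment before a scheduled visit is a non-responder for MMR at that visit. Under section 10.5.2, discontinuation for any reason is also a TTF event. An MMR reached before the stop still counts for the rates of MMR by a time point.

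There is also a cost to the patient. After discontinuation the patient moves to survival follow-up (section 7.1.6). A bosutinib patient stopped for cytopenia alone does not meet the condition for switching to asciminib, which requires treatment failure (section 7.1.2.2).

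**Working it through.** The plan states no figure on this point, so the check is a comparison of texts followed by two short pieces of arithmetic.

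**Step 1: what each text requires for Grade 3/4 cytopenia.** Assume that the hold begins with the cytopenia.

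| Days on hold | Table 6-2 header | Section 6.3.1 and hematologic sub-header |
|---|---|---|
| Up to 28 | No stop required | No stop required |
| 29 to 42 | Must discontinue | May stay on hold and resume on recovery |
| More than 42 | Must discontinue | Must discontinue |

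The conflict is confined to days 29 to 42, a window of 42 − 28 = 14 days.

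**Step 2: which limit is intended.** The Amendment 3 rationale says that "the recovery period for cytopenias has been extended from 28 to 42 days in order to allow for sufficient time to recover". I use this only as evidence of intent. The contradiction lies within the current text and would exist without the amendment history. The header's 28 days matches the earlier cytopenia limit, so it appears not to have been updated.

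**Step 3: effect on one patient's TTF.**
- If the patient would have recovered by day 42 and had no later TTF event, a stop under the header adds an event.
- If the patient would have recovered but had a TTF event later, the stop brings the event date forward.
- If the patient would not have recovered by day 42, no event is added. Its date moves from day 43 to day 29, which is 43 − 29 = 14 days earlier.

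**Step 4: what can still be protected.** The Amendment 03-US.01 rationale, dated 05-Aug-2020, gives 22-Oct-2019 as the end of recruitment. Assume that the last first dose was close to that date.
- 22-Oct-2019 + 24 weeks (168 days) = 07-Apr-2020, before this version.
- 22-Oct-2019 + 96 weeks (672 days) = 24-Aug-2021, about a year after it.

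A correction made at this version therefore comes too late for Week 24. It can still prevent stops that bear on Week 96, on TTF and on patients treated in the switch phase.

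**The case against.** The best reply is that the specific rule overrides the general one. Section 6.3.1 states the 42-day limit just before the table and describes the table as a summary. The hematologic sub-header states the limit again, just below the header. A site would have to overlook both to stop a patient wrongly, and nothing in the documents shows that any site did. This reply stands as far as frequency goes: most careful readers would apply 42 days.

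It does not remove the contradiction. The protocol gives no order of precedence for Table 6-2, although section 14 does give one for drugs that appear on both medication lists. Section 6.3.1 also sends the reader to Table 6-2 for the events that require permanent discontinuation, and section 12 permits no authorized deviations. Between days 29 and 42 a site cannot follow both texts.

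A reader might infer that the header carries more weight because it recurs down the table. The documents do not support that. It is one header row carried across pages, and most of its appearances stand above non-hematologic rows, where 28 days is correct under section 6.3.1. Only where it stands above cytopenia rows does it conflict.

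**Conclusion.** The inconsistency is real and sits in a mandatory stopping rule. It affects patients held for Grade 3/4 cytopenia for 29 to 42 days, and only at a site that applies the header rather than the 42-day rule. The protocol gives no rate of Grade 3/4 cytopenia or duration of holds for this trial, so the number of patients cannot be derived. It is probably small, because the specific rule is stated twice. Sample size and alpha are unaffected.

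Two stronger conclusions are tempting. A reader might infer that the Week 24 comparison is biased. The documents show no stop made under the header, and so give no basis for that claim. A reader might also infer, because the trial is open-label, that sites chose between 28 and 42 days differently by arm. Nothing in the documents shows that this happened, or in which direction.

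What remains is a wording error whose correction is worth making for the sake of later treatment, Week 96 and TTF. The timing rests on the assumption that the last first dose came close to the end of recruitment. Including the switch phase assumes that Table 6-2 also governs dosing there, as no separate dose-modification table is given.

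**What to change.** Change the Table 6-2 header so that the limit reads: *> 28 days for each non-hematologic toxicity (for Grade 3/4 cytopenia see the 42-day rule)*. Make the change wherever the header row is printed. Notify sites that the 42-day rule governs Grade 3/4 cytopenia in both arms.

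The cost is a few words in one table header and a letter to sites. Eligibility, sample size, alpha and the planned analyses do not change.

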Grade 4 (PLT < 25 x 10 ⁹ /L)	Mandatory: Hold dose until resolved to ≤ Grade 2 (recheck CBC 2x/week), then: if resolved in ≤ 14 days, then maintain dose level if resolved in > 14 days, then reduce dose ↓ 1 dose level	Mandatory: Hold dose until resolved to ≤ Grade 2 and neutrophils ≤ Grade 2 (recheck CBC 2x/week), then: if resolved in ≤ 14 days, then maintain dose level if resolved in > 14 days, then reduce dose ↓ 1 dose level
Recurrence of all cytopenias	Recommendation: Hold dose until resolved to ≤ Grade 2, then maintain current dose level.	Recommendation: Hold dose until resolved to ≤ Grade 2, then reduce dose ↓ 1 additional level
Non-hematologic adverse reactions except where further specified in individual sections		
Grade 1	Recommendation: Maintain dose level	Recommendation: Maintain dose level
Grade 2	Recommendation: Hold dose until resolved to ≤ Grade 1, then maintain dose level	Recommendation: Maintain dose level
Grade 3	Mandatory: Hold dose until resolved to ≤ Grade 1, then reduce dose ↓ 1 dose level	Mandatory: Hold dose until resolved to ≤ Grade 1, then reduce dose ↓ 1 dose level, If clinically appropriate, re-escalation of the dose back to baseline dose level (500 mg) should be considered
Grade 4	Mandatory: Permanently discontinue patient from study drug treatment.	Mandatory: Hold dose until resolved to ≤ Grade 1, then reduce dose ↓ 1 dose level; If clinically appropriate, re-escalation of the dose back to baseline dose level (500 mg) should be considered
Investigations (Renal)		
Serum creatinine		
Grade 1 (> ULN - 1.5 x ULN)	Recommendation: Maintain dose level	Recommendation: Maintain dose level
Grade 2 (> 1.5 - 3.0 x ULN)	Recommendation: Hold dose until resolved to ≤ Grade 1 or baseline, then maintain dose level	Recommendation: Hold dose until resolved to ≤ Grade 1 or baseline, then maintain dose level
Grade 3 (> 3.0 - 6.0 x ULN)	Mandatory: Permanently discontinue patient from study drug treatment.	Mandatory: Permanently discontinue patient from study drug treatment.
Grade 4 (> 6.0 x ULN)	Mandatory: Permanently discontinue patient from study drug treatment.	Mandatory: Permanently discontinue patient from study drug treatment.

[figure not shown]
Dose modifications for both asciminib and bosutinib		
Please note that if a patient requires a dose interruption of > 28 days for each toxicity, then the patient must be discontinued from the study treatment		
Worst toxicity CTCAE Grade 4.03	Asciminib	Bosutinib
Investigations (Hepatic)		

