Asciminib dose reduction below total daily 40 mg is not allowed. 20 mg tablets will be dispensed to patients in the instance of dose reduction.			
Dose reduction*			
	Starting dose level – 0	Dose level – 1	Dose level – 2
Bosutinib QD	500 mg (1-500 mg tablet QD)	400 mg (4-100 mg tablets QD)	300 mg (3-100 mg tablets QD)
* Dose reduction should be based on the worst toxicity demonstrated at the last dose.			
Bosutinib dose reduction below total daily 300 mg is not allowed. 100 mg tablets will be dispensed to patients in the instance of dose reduction.			

[figure not shown]

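### Table 6-2 gives conflicting dose instructions for some recurrent Grade 3/4 cytopenias without saying which row governs, and some of its reductions have no permitted level in Table 6-3

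*Combined protocol and SAP*

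**What the plan says.** Section 6.3.1 separates recommended dose changes, offered as help to the investigator, from mandatory ones. Deviations from mandatory "dose interruptions and/or reductions are not allowed and mandatory interruptions or reductions must be strictly followed".

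For cytopenias, Table 6-2 then contains:

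- **Grade 3 and Grade 4 neutropenia and thrombocytopenia, both drugs, Mandatory.** Hold until Grade 2 or better (on bosutinib the other cell line must also be there). Then "if resolved in ≤ 14 days, then maintain dose level", but "if resolved in > 14 days, then reduce dose ↓ 1 dose level". Nothing confines these rows to a first episode.
- **Febrile neutropenia, both drugs, Mandatory.** Hold until resolved, then go down one level, whatever the recovery time.
- **Recurrence of all cytopenias, Recommendation.** Asciminib: "Recommendation: Hold dose until resolved to ≤ Grade 2, then maintain current dose level". Bosutinib: "Recommendation: Hold dose until resolved to ≤ Grade 2, then reduce dose ↓ 1 additional level". There is no grade trigger and no time limit.

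The only sentence in Section 6.3.1 that sets recurrent cytopenias apart concerns stopping treatment. A patient must discontinue if, after resuming at a lower dose, "the toxicity recurs with the same or worse severity, except for recurrence of cytopenias".

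Table 6-3 gives asciminib two levels (40 and 20 mg BID) and bosutinib three (500, 400 and 300 mg QD). It states "Bosutinib dose reduction below total daily 300 mg is not allowed", with a matching bar for asciminib below 40 mg a day in total.

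**The concern.** A second Grade 3 or Grade 4 episode meets both a graded row and the recurrence row, and the protocol gives no order of precedence. Where the two differ, a site cannot follow both. Even the hold is compulsory in one row and advisory in the other. Some of the reductions also lead to a level that does not exist.

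This bears first on patients, whose dose after a recurrence depends on which row the site reads. It also bears on the data. Section 10.3 summarises dose intensity, relative dose intensity and dose adjustments. Section 10.5.3.6 assesses tolerability by counting patients with interruptions and reductions. The recurrence row differs between the arms and the trial is open-label, so inconsistent handling need not cancel out. Section 12 permits no authorised deviations and has significant ones reported in the CSR, yet whether some dosing decisions count as deviations depends on the row chosen.

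**Working it through.** There is no planned figure to reproduce. The check lists every combination of arm, dose level (Table 6-3) and recovery time for a recurrent Grade 3/4 neutropenia or thrombocytopenia, and sets the two Table 6-2 instructions side by side.

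| Drug and current level | Recovery | Graded row (Mandatory) | Recurrence row (Recommendation) | Result |
|---|---|---|---|---|
| Asciminib 40 mg BID | ≤ 14 days | maintain | maintain | agree |
| Asciminib 40 mg BID | > 14 days | reduce | maintain | **conflict** |
| Asciminib 20 mg BID | ≤ 14 days | maintain | maintain | agree |
| Asciminib 20 mg BID | > 14 days | reduce (no level) | maintain | **conflict** |
| Bosutinib 500 or 400 mg | ≤ 14 days | maintain | reduce | **conflict** |
| Bosutinib 500 or 400 mg | > 14 days | reduce | reduce | agree |
| Bosutinib 300 mg | ≤ 14 days | maintain | reduce (no level) | **conflict** |
| Bosutinib 300 mg | > 14 days | reduce (no level) | reduce (no level) | agree, but neither can be done |

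1. By arm and recovery time, two of the four cases conflict: asciminib > 14 days and bosutinib ≤ 14 days.
2. In all four cases the hold is mandatory under the graded row and recommended under the recurrence row.
3. Febrile neutropenia stands in the neutropenia block, so its recurrence is taken here as a recurrent cytopenia. On asciminib the result is a mandatory reduction against a recommendation to maintain. On bosutinib both rows reduce.
4. At the lowest level, the mandatory > 14-day reduction has no permitted step for either drug (asciminib 20 mg BID, bosutinib 300 mg). The bosutinib recurrence reduction has none at 300 mg, whatever the recovery time. No passage states what follows.

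Dose at issue where a lower level exists:

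- Asciminib: 2 × 40 = 80 mg a day against 2 × 20 = 40 mg a day, a difference of half the daily dose.
- Bosutinib: 500 − 400 = 100 mg, or 400 − 300 = 100 mg.

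Effect of one patient counted or not counted as a dose reduction, with the planned arm sizes in Section 10.8: 1/148 = 0.68 percentage points for asciminib and 1/74 = 1.35 points for bosutinib.

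**The case against.** The best defence is that a specific row overrides a general one. Table 6-2 has a dedicated recurrence row, its bosutinib cell speaks of an additional level, and Section 6.3.1 points to the table for recurrent cytopenias. A site could reasonably treat the graded rows as first-episode rules. But the documents do not say so. The exemption in Section 6.3.1 covers compulsory discontinuation only. This reading would also let a recommendation displace a mandatory instruction and make the hold for a recurrent Grade 4 event advisory. The ambiguity stands.

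Other objections do limit the point:

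- **A reader might infer that the rows contradict each other throughout.** They do not. In two of the four cases both give the same direction.
- **A reader might infer that no permitted action remains at bosutinib 300 mg.** The recurrence row is only a recommendation. For recovery within 14 days the graded row says maintain. Section 6.1.5 leaves discontinuation to the investigator's discretion. What is missing is a stated action, chiefly for recovery beyond 14 days.
- **A reader might infer that following the bosutinib recurrence row breaches a mandatory rule.** Section 6.3.1 protects mandatory interruptions and reductions, and maintaining a dose is neither. The breach is clear only where a mandatory reduction is not made, as on asciminib after more than 14 days, or where the hold is treated as optional.
- **Mixed status is not in itself an error.** The bosutinib transaminase and diarrhea rows pair a mandatory hold with recommended follow-up. The fault here is two statuses for one step.

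**Conclusion.** The point holds within limits. Table 6-2 gives conflicting dose instructions for asciminib recurrences resolving in more than 14 days, bosutinib recurrences resolving in 14 days or less, and recurrent febrile neutropenia on asciminib. It gives the hold two statuses. At the lowest level of each drug it calls for reductions that Table 6-3 rules out, with no stated next step. This rests on the graded and febrile rows applying to repeat episodes, which their wording allows and nothing in the documents excludes.

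The number of patients affected is unknown. Section 1.2.1.2 lists thrombocytopenia and neutropenia among the adverse events seen in more than 10% of 35 patients on 40 mg BID, but says nothing about recurrence or recovery time at Grade 3/4. A reader might assume that 5–15% of the 222 planned patients have such a recurrence and arrive at 11–33 affected. That rate is not in the documents, and even if it were right the count would be an upper bound, because many recurrences would fall where the rows agree.

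A reader might also infer damage to the Week 24 endpoint. Nothing in the documents links these dose differences to MMR at Week 24. The supported consequence is uneven dosing across sites and less interpretable dose-reduction and dose-intensity summaries, which are descriptive.

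**What to change.** Reconcile the graded neutropenia and thrombocytopenia rows, the febrile neutropenia row and the recurrence row of Table 6-2 with each other, with the lowest levels in Table 6-3, and with the exemption in Section 6.3.1. After the change, each recurrence should fall under one stated instruction. Each step of it should have one stated status, mandatory or recommended, and the text should say what follows when a reduction is called for at the lowest level. Which dosing rule applies is for the sponsor's clinical team.

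The cost is wording in Table 6-2 and Section 6.3.1, issued to sites as a written amendment under Section 12.1. No visit, test or sample is added. Recruitment ended on 22 October 2019, so by the amendment of 5 August 2020 a change could no longer alter dosing before Week 24 (24 weeks from the end of recruitment is early April 2020). It would still serve patients on treatment, because Section 4.3 lets treatment run to 96 weeks after the last patient's first dose, or longer with switching.
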